#### 6.5. Baseline and Other Summaries and Analyses

##### 6.5.1. Baseline Summaries

A breakdown of demographic data will be provided for age, race, weight, body mass index and height. Each will be summarized by sex at birth and 'All Subjects' with tables and listings presented in accordance with the Pfizer Data Standards. Use geriatric age categories for the demographic summaries (<65, 65-74, 75-84, and ≥85).

Also, medical history and primary diagnosis will be tabulated and listed in accordance with the Pfizer Data Standards.

CCI [REDACTED]

- [REDACTED]
- [REDACTED]
- [REDACTED]
- [REDACTED]
- [REDACTED]
- [REDACTED]
- [REDACTED]
- [REDACTED]

**C** [REDACTED]  
**C** [REDACTED]  
[REDACTED]  
[REDACTED]

### 6.5.2. Study Conduct and Subject Disposition

Data will be reported in accordance with Pfizer Data Standards

### 6.5.3. Study Treatment Exposure

Duration of exposure will be presented in tables and listings in accordance with the Pfizer Data Standards.

A maintenance dose is defined as the dose a subject has continued at least for the last 4 weeks (see [Section 4.2](#)) during the maintenance period.

A summary will be prepared for the number of subjects who discontinue the treatment before the dose maintenance period, their final dose, and reason for drop outs.

For those who reached the dose maintenance period, a summary will be prepared of the number and percent of patients by final dose received, the maintenance dose, and the number of dose adjustments per patient until the final dose received. Their disposition will also be summarized by the maintenance dose including all subjects who did not reach a maintenance dose. Time to reach the maintenance dose (defined as 15+ weeks for subjects who never reached a maintenance dose) will be summarized by the maintenance dose within each treatment. A separate summary of disposition at the end of each subject's titration (reached the maintenance dose or not) will also be provided by their dose at the end of titration.

Compliance will be calculated and summarized across the whole double-blind treatment phase, and by visit. Compliance will be based on the dosing record, and calculated as:

$$\text{Compliance} = \text{Actual Dosing} / \text{Expected dosing} \times 100\%.$$

### 6.5.4. Concomitant Medications and Non-Drug Treatments

All prior and concomitant medication(s) as well as non-drug treatment(s) will be provided in tables and listings in accordance with the Pfizer Data Standards. Prior and concomitant anti-PD medication use (including prior exposure to dopaminergic treatments) including prior exposure to dopaminergic treatments) will also be separately summarized.

## 6.6. Safety Summaries and Analyses

The safety analysis set is the primary population for the safety summaries and analyses.

### 6.6.1. Adverse Events

Adverse events will be listed and summarized within treatment group in accordance with the Pfizer Data Standards.

The details of Tier-1, Tier-2 and Tier-3 AEs are described in [Section 3.5.1](#).

Adverse events within Tier-1 and -2 will be summarized using Risk Differences between each PF-06649751 group and placebo, together with 95% CI. A graphical presentation of the percentage of subjects with each AE and Risk Difference (with 95% CI) ordered by decreasing risk difference will be shown for the Tier-1 and -2 AEs separately. Significance tests will be performed for the Tier-1 adverse events. There will be no multiplicity adjustment for these significance tests.

For Tier-1 and Tier-2 adverse event outputs, the following footnotes will be used: “P-values and confidence intervals are not adjusted for multiplicity and should be used for screening purpose only. The 95% Confidence intervals are provided to help gauge the precision of the estimates for Risk Difference. Risk Difference is computed as PF-06649751 versus Placebo.”

Tier-1 events for risk difference and relative risk will use unconditional exact methods (an approach proposed by Chan and Zhang, 1999) based on standardized statistics. For Tier-2 events, an asymptotic approach will be performed.

The Tier-3 adverse events will be described as part of the overall AE summary.

It should be recognized that most studies are not designed to reliably demonstrate a causal relationship between the use of a pharmaceutical product and an adverse event or a group of adverse events. Except for select events in unique situations, studies do not employ formal adjudication procedures for the purpose of event classification. As such, safety analysis is generally considered as an **CCI** analysis and its purpose is to generate hypotheses for further investigation. The 3-tier approach facilitates this **CCI** analysis.

### 6.6.2. Laboratory Data

Laboratory data will be listed and summarized within treatment group in accordance with the Pfizer Data Standards.

Incidence of laboratory test abnormalities (including without regard to baseline abnormality) will be summarized within each treatment group.

### 6.6.3. Vital Signs (Blood Pressure and Pulse Rate)

For each planned time point, baseline values and change from baseline values within each treatment will be summarized with descriptive statistics (using Pfizer Data Standards). A plot of individual blood pressure versus plasma concentration will be generated.

Maximum decrease and increase values and changes from baseline for vital signs (for supine and standing) will also be summarized descriptively within treatment group using categories as defined in the Pfizer Data Standards. Numbers and percentages of subjects meeting the categorical criteria will be provided. All planned and unplanned post-dose time points will be counted in these categorical summaries. All values meeting the criteria of potential clinical concern will be listed.

Vital signs collected at additional positions will be listed only.

The following non-standard safety tables will be included:

- A summary of postural change from supine to standing systolic and diastolic blood pressures.
- Incidence of subjects with orthostatic hypotension (defined in [Section 3.5.3](#) above), for each visit, last visit and any post-baseline incidence or orthostatic hypotension or minimum absolute change in postural blood pressure.

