20. A decrease in systolic blood pressure (BP) of  $>20$  mmHg or in diastolic BP of  $>10$  mmHg measured 2 minutes after changing from a supine to standing position in the presence of symptoms of orthostasis. In the absence of symptoms of orthostasis a decrease in systolic blood pressure (BP) of  $>30$  mmHg or in diastolic BP of

- >15 mmHg measured 2 minutes after changing from a supine to standing position (The mean of three independent sets of vital signs, taken at least 15 minutes apart at the screening visit, will determine eligibility).
21. 12-lead ECG demonstrating QTcF >450 msec (>470 msec for females) or a QRS interval >120 msec at screening. If QTcF exceeds 450 msec (470 msec for females), or QRS exceeds 120 msec, the ECG should be repeated two more times and the average of the three values should be used to determine the subject's eligibility.
  22. Subjects with **ANY** of the following abnormalities in clinical laboratory tests at screening, as assessed by the study-specific laboratory and confirmed by a single repeat, if deemed necessary:
    - Aspartate transaminase (AST)/ serum glutamic oxaloacetic transminase (SGOT) **or** alanine transaminase (ALT)/ serum glutamic pyruvic transminase (SGPT)  $\geq 2$  x upper limit of normal (ULN).
    - Total bilirubin  $\geq 1.5$  x ULN; subjects with a history of Gilbert's syndrome may have a direct bilirubin measured and would be eligible for this study provided the direct bilirubin is  $\leq$  ULN.
  23. A positive urine drug screen for drugs of abuse unless explained by medically indicated medication.
  24. A positive test for hepatitis B surface antigen or hepatitis C antibody (if confirmed by positive hepatitis C virus-ribonucleic acid (HCV-RNA) test).

General and Administrative:

25. Subjects who are investigational site staff members directly involved in the conduct of the study and their family members, site staff members otherwise supervised by the investigator, or subjects who are Pfizer employees directly involved in the conduct of the study.
26. Treatment with an investigational drug within 30 days (or as determined by the local requirement) or 5 half-lives preceding the first dose of study medication (whichever is longer).
27. Blood donation (excluding plasma donations) of approximately 1 pint (500 mL) or more within 56 days prior to Visit 1 (Randomization).
28. Unwilling or unable to comply with the lifestyle requirements described in [Section 4.4](#) this protocol.

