### 3.5.3. Vital Signs (Blood Pressure and Pulse Rate)

*Blood pressure and pulse rate will be measured at times specified in the STUDY PROCEDURES section of this protocol. Additional collection times, or changes to collection times of blood pressure and pulse rate will be permitted, as necessary, to ensure appropriate collection of safety data.*

*Orthostatic hypotension is defined as a decrease of  $\geq 20$  mmHg for systolic blood pressure or  $\geq 10$  mmHg for diastolic blood pressure 2 minutes after standing from a supine position. Orthostatic hypotension may be symptomatic or asymptomatic.*

Baseline will be the Day -1/Rand measurement.

Determine if there is any blood pressure or pulse rate data abnormalities of potential clinical concern as defined in Pfizer Data Standards.

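### The orthostatic hypotension table in SAP 6.6.3 does not separate subjects who already met the definition at Day -1 from new cases

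*SAP*

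**What the plan says.** **Definition.** SAP 3.5.3, repeating protocol 7.2.5: "Orthostatic hypotension is defined as a decrease of $\geq 20$ mmHg for systolic blood pressure or $\geq 10$ mmHg for diastolic blood pressure", measured two minutes after the subject stands up. It adds: "Orthostatic hypotension may be symptomatic or asymptomatic".

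**Entry.** Protocol 4.2, exclusion 20, sets two limits. With symptoms of orthostasis, a subject is excluded for a fall above 20 mmHg systolic or above 10 mmHg diastolic. Without symptoms, the limits are higher: above 30 mmHg for the systolic fall and, for the diastolic fall, ">15 mmHg measured 2 minutes after changing from a supine to standing position". Screening values decide eligibility.

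**Table.** SAP 6.6.3 introduces two outputs with "The following non-standard safety tables will be included". The second is the incidence of subjects with orthostatic hypotension, "for each visit, last visit and any post-baseline incidence or orthostatic hypotension or minimum absolute change in postural blood pressure". The phrase is slightly garbled, but its plain sense is a count at each visit, at the last visit and at any post-baseline visit. No denominator of baseline-negative subjects, new-onset rule or shift table is given.

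**Baseline.** SAP 3.5.3 states "Baseline will be the Day -1/Rand measurement". The Schedule of Activities has supine and standing readings at Visit 1.

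**Contrast.** SAP 5.2.1 attaches a drug-placebo difference in rates, with a 90% confidence interval, to binary outputs.

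**The concern.** The entry limits are looser than the definition, so some randomized subjects may already be cases. The table then counts them again after baseline as if they were informative about the drug. Over many visits a pre-existing case is likely to be counted in either arm, which adds to both rates and carries little information on the treatment difference.

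Elsewhere the SAP does deal with baseline. Adverse events must be new or more severe than before treatment (3.5.1). The C-SSRS has new-onset and worsening definitions, and its new-onset denominator is limited to subjects without suicidality at baseline (3.5.7, 6.6.7). The laboratory section states how baseline abnormality is handled (6.6.2). The orthostatic hypotension table is silent, and because it is labelled non-standard, the sponsor's data standards cannot be presumed to supply the rule.

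Postural effects are of interest for this drug: protocol 1.4.2 says orthostatic hypotension seemed more common at higher doses in the single-dose patient study. With about 44 subjects per arm, contrast should not be given away needlessly.

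**Working it through.** The documents state no expected rate of orthostatic hypotension for this trial, so there is no planned figure to reproduce.

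**1. Overlap of limits (fall in mmHg, systolic or diastolic)**

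| | Counts as orthostatic hypotension | Excluded at entry | Eligible and already a case |
|---|---|---|---|
| No symptoms | ≥20 or ≥10 | >30 or >15 | 20–30 systolic or 10–15 diastolic, with neither upper limit exceeded |
| Symptoms | ≥20 or ≥10 | >20 or >10 | exactly 20 or exactly 10, with neither limit exceeded |

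**2. Chance that a pre-existing case is counted.** The Schedule of Activities has postural readings at nine post-baseline visits (2, 3, 4, 6, 8, 10, 12, 14 and 15). Suppose a pre-existing case is positive at a fraction v of visits, independently between visits (an assumption). The chance of at least one positive is 1 − (1 − v)^9:
- v = 0.3: 1 − 0.7^9 = 0.96
- v = 0.5: 1 − 0.5^9 = 0.998

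**3. Effect on the any-post-baseline row.** Let π be the proportion positive at Day -1, q the chance that such a subject is counted after baseline, and p the new-onset risk. Then

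tabulated risk = πq + (1 − π)p.

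If q is the same in both arms it cancels, and

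tabulated risk difference = (1 − π) × new-onset risk difference.

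**4. Illustration.** Assumed, not in the documents: π = 10%, 20% or 30%; p = 6% on placebo and 20% on drug; q = 1. The new-onset difference is 20 − 6 = 14 points. Half-widths of the 90% interval use 1.645 × √[(r0(1 − r0) + r1(1 − r1))/n]. For the all-subject table n = 44 per arm (protocol 9.1). For baseline-negative subjects n = 44(1 − π), with risks 6% and 20%.

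| π | Placebo, tabulated | Drug, tabulated | Difference (points) | Loss (points) | Half-width, all subjects | Half-width, baseline-negative |
|---|---|---|---|---|---|---|
| 0% | 6.0% | 20.0% | 14.0 | – | – | – |
| 10% | 0.10 + 0.90 × 0.06 = 15.4% | 0.10 + 0.90 × 0.20 = 28.0% | 12.6 | 1.4 | 14.3 | 12.2 |
| 20% | 0.20 + 0.80 × 0.06 = 24.8% | 0.20 + 0.80 × 0.20 = 36.0% | 11.2 | 2.8 | 16.0 | 12.9 |
| 30% | 0.30 + 0.70 × 0.06 = 34.2% | 0.30 + 0.70 × 0.20 = 44.0% | 9.8 | 4.2 | 17.0 | 13.8 |

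Under these assumptions the baseline-negative analysis has both a larger difference and a narrower interval, in spite of its smaller denominator.

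**5. When the attenuation fails.** The factor (1 − π) needs equal q in both arms. At a single visit there is no ceiling, and the drug could worsen pre-existing cases. With π = 20% and q of 0.3 on placebo and 0.8 on drug (assumed), the difference is 0.20 × 0.5 + 0.80 × 0.14 = 21.2 points, which is more than 14.

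**The case against.** - **Baseline is not ignored in SAP 6.6.3.** The section gives baseline values, changes from baseline, maximum changes and a summary of postural change. The each-visit rows may include Visit 1 and so show baseline prevalence. This stands as partial mitigation. None of these outputs identifies who newly crosses the definition.
- **Adverse events are already filtered.** Orthostatic hypotension reported as an adverse event passes the treatment-emergent rule and, at 1% or more in either arm, gets a risk difference with a 95% interval (SAP 3.5.1, 6.6.1). This is true, but protocol 8.5 does not require an asymptomatic abnormal finding to be reported unless it leads to further testing, treatment or a dosing change, or is judged to be an event. Asymptomatic falls are the main overlap group.
- **The prior signal is thin.** The rates in protocol 1.4.2 (5.9% on placebo, 8.3% at 3 mg, 33.3% at 6 mg) are adverse-event rates after single doses: 1 of 17, 1 of 12 and 2 of 6. None is listed for 9 mg, and maximum falls in blood pressure were similar between groups. They should not be read as measured rates under the 20/10 definition.
- **The loss is small on the planned scale.** It is 1.4 to 4.2 points against half-widths of 14 to 17 points. A reader might quote risk ratios instead (3.3 falling to 1.8, 1.45 or 1.3 in the same illustration), but the SAP plans relative risk only for Tier-1 adverse events, and none are defined. This objection stands and limits the weight of the point.
- **The table is descriptive.** No decision rule uses it, and SAP 6.6.1 treats safety analysis as hypothesis-generating. This also stands.

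**Conclusion.** The point holds as a gap in a descriptive safety table. The overlap between entry limits and definition is in the text, and the any-post-baseline row, followed as written, mixes pre-existing with new cases. Incidence is inflated in both arms. With equal persistence across arms the risk difference shrinks by (1 − π): from 14 points to between 12.6 and 9.8 in the illustration. The factor follows from the algebra. The size rests on assumed prevalence and new-onset risks and cannot be fixed from the documents.

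Four stronger readings are not supported:
- A reader might infer that the SAP instructs counting regardless of baseline. It is silent on this.
- A reader might call the counts on-treatment. The SAP says post-baseline, and Visit 15 comes about two weeks after the last dose.
- A reader might infer that the table would show mostly disease-related falls. That depends on a prevalence the documents do not give.
- A reader might infer bias towards a false signal. Randomization balances pre-existing cases in expectation. The single-visit rows need not be attenuated at all if the drug worsens pre-existing cases.

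**What to change.** In SAP 6.6.3, using the Day -1 supine and standing values:

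1. Report the prevalence of orthostatic hypotension at Day -1 by arm.
2. Report any-post-baseline orthostatic hypotension among subjects without it at Day -1, with the difference and 90% interval from SAP 5.2.1.
3. Add a shift table for all subjects from Day -1 status to worst post-baseline status, so that worsening of pre-existing cases is visible.
4. Keep the current table as support, and state whether its any-post-baseline row includes the off-drug Visit 15.

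The cost is SAP wording and a few extra outputs from data already collected. Item 2 has a slightly smaller denominator. Some misclassification will remain: Day -1 is one scheduled assessment, so an intermittent case that is negative that day would be labelled new over nine later visits. No change to the entry limits, the definition or any clinical rule is proposed.

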### 6.6.4. Electrocardiogram

For each planned time point, baseline values, raw values and change from baseline values within each treatment will be summarized with descriptive statistics for each ECG parameter (using Pfizer Data Standards).

A plot of QTcF versus plasma concentration will be generated at nominal time points. Maximum decrease and increase values and changes from baseline for the ECG parameters QT interval, heart rate, QTc interval, PR interval and QRS interval will be summarized by treatment and time post dose using Pfizer Data Standards.

The number (%) of subjects with maximum post dose QTc values and maximum increases from baseline in the following categories will be tabulated by treatment:

**Table 5. Safety QTcF**

	Borderline (msec)	Prolonged (msec)
Absolute Value	≥450 - <480	≥480
Absolute Change	30-<60	≥60

In addition, the number of subjects with corrected and uncorrected QT values ≥500 msec will be summarized.

ECG endpoints and changes from baseline (QTcF, PR, QRS) will also be summarized descriptively by treatment using categories as defined in Pfizer Data Standards (for QTc, these correspond to ICH E14). Numbers and percentages of subjects meeting the categorical criteria will be provided. All planned and unplanned post dose time points will be counted in these categorical summaries. All values meeting the criteria of potential clinical concern will be listed.

#### **6.6.5. Physical Examination**

Physical examination data will be listed and summarized within treatment group in accordance with the Pfizer Data Standards. Summary of new/intensified physical examination findings from Baseline to Week 15 will also be presented.

#### **6.6.6. Neurological Examination**

Summary of new/intensified neurological examination findings from Baseline to Week 15 will be presented. Otherwise, neurological examination data will be presented in the listings.

#### **6.6.7. Columbia Suicide Severity Rating Scale (C-SSRS)**

In general, the denominator used in the percentages will be the number of subjects assessed for suicidality or worsening, the denominator would include the subset of subjects who had any level of suicidality reported at baseline. For new onset, the denominator would include the subset of subjects with no suicidality reported at baseline.

A subject listing of C-CASA categories as well as the underlying C-SSRS scale data will be presented.

In addition, a summary table with the number and percent of subjects within each C-CASA category by treatment group at screening, baseline, and at any time post-baseline without regard to baseline will be reported.

#### **6.6.8. Questionnaire for Impulsive-Compulsive Disorders in Parkinson's Disease – Rating Scale (QUIP-RS)**

For each planned time point and item (ie, disorder), baseline values, raw values and change from baseline values within each treatment will be summarized with descriptive statistics.

#### **6.6.9. Physician Withdrawal Checklist (PWC-20)**

Summaries of the count and percentage of patients experiencing each symptom and severity listed in the PWC-20 will be provided by treatment group. Follow the PDS used for reporting incidence and severity of Adverse Events.

The Total PWC-20 score will be presented by treatment group using continuous summary statistics for the raw data.

## 7. INTERIM ANALYSES

### 7.1. Introduction

*Up to one interim analysis will be performed when approximately 28 randomized subjects (32% total sample size) have finished their double-blind treatment period in the study, and efficacy data have been collected, databased and cleaned. The purpose of this interim analysis will be to assess study futility and to aid future development planning. If an interim analysis is performed, the study will continue whilst the analysis is being conducted.*

### 7.2. Interim Analyses and Summaries

*Before any interim analysis is initiated, the details of the objectives, decision criteria, unblinding, dissemination plan and method of maintaining the study blind as per Pfizer's standard operating procedures (SOPs) will be documented and approved in an internal review committee (IRC) charter.*

In addition, the analysis details will be documented and approved in a separate interim analysis SAP.

**9. APPENDICES**

**Appendix 1. SUMMARY OF EFFICACY ANALYSES**

Endpoint	Analysis Set	Statistical Method	Missing Data	Interpretation
MDS-UPDRS Parts III, Week 15	FAS	MMRM	OC	Primary Analysis
MDS-UPDRS Parts III, Week 15	FAS-by geographic region	MMRM	OC	Subset Analysis*
MDS-UPDRS Parts III, Week 15	FAS-by concomitant Parkinson's Disease medication at randomization (NO/YES)	MMRM	OC	Subset Analysis*
MDS-UPDRS Parts III, Week 15	FAS-by prior dopaminergic anti-PD med exposure (NO/YES)	MMRM	OC	Subset Analysis*
MDS-UPDRS Parts III, Week 15	FAS-by level of subjects' maintenance doses (<3 mg or ≥3 mg)	MMRM	OC	Subset Analysis*
MDS-UPDRS Parts III, Week 15	PPAS	MMRM	OC	Sensitivity Analysis
MDS-UPDRS Parts III, All Other Visits	FAS	MMRM	OC	Secondary Analysis
MDS-UPDRS Parts I, II, IV, and total score, All Visits	FAS	MMRM	OC	Secondary Analysis
CCI [REDACTED]	FAS	MMRM	OC	CCI [REDACTED] Endpoints
[REDACTED]	FAS	CMH	LOCF	CCI [REDACTED] Endpoints

\*Only subgroups that have ≥10% of total subjects will be analyzed.

090177e18fca9a96\Approved\Approved On: 19-Nov-2018 07:48 (GMT)

CCI
